7.1.3.3 HIV Evaluation

The following specimens are to be obtained for HIV evaluation:

- Blood must be drawn from each subject to assess HIV RNA plasma levels at screening as shown in the Trial Flow Chart (Section 6.0). HIV RNA in plasma will be measured using a COBAS™ AmpliPrep/COBAS™ TaqMan HIV-1 Test, version 2.0® assay with a LLOQ of 20 IU/mL.
- Blood must be drawn from each subject to assess immunologic status. CD4+ T-cell counts will be obtained at screening as shown in the Trial Flow Chart (Section 6.0).

The following nomenclature will be used when describing HIV RNA levels:

- HIV-1 RNA < LLOQ, Target Not Detected
- HIV-1 RNA < LLOQ, Target Detected
- HIV-1 RNA IU/mL

7.1.3.4 HBV Evaluation

- Blood must be drawn from each subject to assess HBsAg, anti-HBc, and anti-HBs at screening.
- For subjects who are anti-HBc positive, HBV DNA will be assessed at screening, and both HBV DNA and HBsAg will be monitored during the trial. The results of these assessments will be used to determine HBV reactivation, which will be reported as an Event of Clinical Interest as specified in Section 7.2.3.2.
- Subjects who develop HBV reactivation will be managed by site investigators according to current treatment guidelines and/or local standard of care.
- Subjects who develop HBV reactivation may continue in the trial at the discretion of the site investigators

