4.2.3.1.1 Measurement of HCV RNA

HCV RNA levels in plasma will be measured on blood samples drawn from each subject at various time points prior to, during, and after dosing, as indicated in the Trial Flow Chart (Section 6.0). Samples are collected and processed as per instructions provided by the central laboratory manual (assay type indicated in central laboratory manual).

Results from the sample collected at the screening visit are used to determine eligibility. Samples collected at other time points are used for efficacy analyses. They are also used to identify subjects who meet virologic failure criteria.

The nomenclature detailed in [Table 9](#) will be used when describing HCV RNA levels:

Table 9 Nomenclature for Describing HCV RNA Levels

Abbreviation	Definition	HCV RNA Level
TND	Target not detected	HCV RNA not detected
TD(u)	Target detected but unquantifiable	HCV RNA < LLOQ
TD(q)	Target Detected, quantifiable	HCV RNA \geq LLOQ

4.2.3.1.1.1 Definition of Efficacy Endpoints

Efficacy will be defined at different time points during the trial. Specific endpoints are:

- SVR₁₂ (sustained virologic response 12 weeks after the end of all study therapy). The subject has HCV RNA < LLOQ (either TD[u] or TND) 12 weeks after the end of all study therapy.
- SVR₂₄ (sustained virologic response 24 weeks after the end of all study therapy). The subject has HCV RNA < LLOQ (either TD[u] or TND) 24 weeks after the end of all study therapy.

4.2.3.1.1.2 Definition of Virologic Failure: Non-Response, Rebound, Virologic Breakthrough and Relapse

Lack of efficacy at different time points in the trial will be categorized as:

- Non-response: Subject has HCV RNA detected at end of treatment without HCV RNA $<$ LLOQ on treatment (note that breakthrough is captured below).
- Rebound: Subject has a rebound defined as $>1 \log_{10}$ IU/mL increase in HCV RNA from nadir while on treatment and confirmed from a separate blood draw within 2 weeks.
- Virologic breakthrough: Subject has a confirmed HCV RNA \geq LLOQ (TD [q]) after being $<$ LLOQ previously while on treatment. Confirmation is defined as an HCV RNA \geq LLOQ from a separate blood draw repeated within 2 weeks.
- Relapse: Subject has a confirmed HCV RNA \geq LLOQ (TD [q]) following end of all study therapy, after becoming undetectable (TND) at end of treatment. Confirmation is defined as an HCV RNA \geq LLOQ from a separate blood draw repeated within 2 weeks.

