6.0 TRIAL FLOW CHART

Treatment Arm	Screen	Treatment Period				Follow Up Period			Unscheduled Visits	
		Day	Week							
Arm 1: 8 weeks	SCR	1 ¹	4	8	NA	FU4	FU12	FU24	HCV VFC Visit	Early DC Visit
Arm 2: 12 weeks	SCR	1 ¹	4	8	12	FU4	FU12	FU24		
Visit Number	1	2	3	4	5	6	7	8	9	10
Visit Window	-45 d	NA	-7 to +7 d	-7 to +14 d	-7 to +14 d	-1 to +2 w	-2 to +2 w	-2 to +2 w	NA	NA
Administrative Procedures										
Informed consent	X									
Informed consent for FBR	X									
Inclusion/exclusion criteria	X	X								
Subject identification card	X									
Medical history	X									
Prior and concomitant medication review	X	X	X	X	X				X	X
Treatment randomization/allocation		X								
Review study medication diary		X	X	X	X					X
Clinical Procedures/Assessments										
PE	X ²	X ²	X ²	X ²	X ²	X ²				X ²
Height		X								
Weight	X	X								
Vital signs	X	X	X	X	X				X	X
Subject confirmation of birth control	X	X	X	X	X	X			X	X
Review AEs ³	X	X	X	X	X	X	X	X	X	X

Treatment Arm	Screen	Treatment Period				Follow Up Period			Unscheduled Visits	
		Day	Week							
Arm 1: 8 weeks	SCR	1 ¹	4	8	NA	FU4	FU12	FU24	HCV VFC Visit	Early DC Visit
Arm 2: 12 weeks	SCR	1 ¹	4	8	12	FU4	FU12	FU24		
Visit Number	1	2	3	4	5	6	7	8	9	10
Visit Window	-45 d	NA	-7 to +7 d	-7 to +14 d	-7 to +14 d	-1 to +2 w	-2 to +2 w	-2 to +2 w	NA	NA
Laboratory Procedures/Assessments										
Coagulation	X	X	X	X	X	X	X	X	X	X
Chemistry & hematology	X	X	X	X	X	X	X	X	X	X
FSH ⁴	X									
Urinalysis		X								
Urine pregnancy test ⁵ (female of childbearing potential only)	X	X	X	X	X	X ⁵			X	X
HBV Evaluations⁶										
HBsAg	X	X	X	X	X	X	X	X		
Anti-HBc	X									
Anti-HBs	X									
HBV DNA	X	X	X	X	X	X	X	X		
HCV Evaluations										
HCV genotype determination	X									
Liver imaging	X ⁷									
HCV RNA level ⁸	X	X	X	X	X	X	X	X	X	X ⁹
Plasma for HCV viral resistance and biomarkers ¹⁰		X				X	X	X	X	X ⁹
Blood for genetic analysis ¹¹		X								

Treatment Arm	Screen	Treatment Period				Follow Up Period			Unscheduled Visits	
		Day	Week							
Arm 1: 8 weeks	SCR	1 ¹	4	8	NA	FU4	FU12	FU24	HCV VFC Visit	Early DC Visit
Arm 2: 12 weeks	SCR	1 ¹	4	8	12	FU4	FU12	FU24		
Visit Number	1	2	3	4	5	6	7	8	9	10
Visit Window	-45 d	NA	-7 to +7 d	-7 to +14 d	-7 to +14 d	-1 to +2 w	-2 to +2 w	-2 to +2 w	NA	NA
HIV Evaluations										
HIV-1 serology	X									
HIV RNA and CD4+ T-Cell Counts (all subjects) ¹²	X									
Drug Administration¹³										
EBR/GZR (open label)		X	X	X ¹⁴	X ¹⁴					

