AE = adverse event; anti-HBc = hepatitis B core antibody; HBsAg = hepatitis B surface antigen; DC = discontinuation; DNA = deoxyribonucleic acid; EBR = elbasvir; EOT = end of treatment; FBR = future biomedical research; FSH = follicle-stimulating hormone; FU = follow-up; GZR = grazoprevir; HBsAg = hepatitis B surface antigen; HCV = hepatitis C virus; HIV = human immunodeficiency virus; IEC = independent ethics committee; IRB = institutional review committee; NA = not applicable; PE = physical examination; RNA = ribonucleic acid; SCR = screening; TW = treatment week; VFC = virologic failure confirmation

¹ Procedures on Day 1 should be performed prior to the first morning dose unless otherwise specified.

² A comprehensive PE will be performed at screening and baseline (Day 1). For all other visits, a focused PE will be conducted when clinically indicated.

³ All AEs that occur after the consent form is signed but before randomization/allocation must be reported by the investigator if they cause the subject to be excluded from the trial, or are the result of a protocol-specified intervention, including but not limited to washout or discontinuation of usual therapy, diet, placebo treatment or a procedure. From the time of randomization/allocation through 14 days following discontinuation of study treatment, all AEs must be reported by the investigator. The reporting timeframe for AEs meeting any serious criteria is described in Section 7.2.3.1.

⁴ For postmenopausal women only, defined as at least 12 months with no menses in women \geq 45 years of age.

⁵ Urine pregnancy test kits will be dispensed to female subjects of childbearing potential so that a pregnancy test can be performed 2 weeks after completing treatment. The test results must be provided to the investigator and/or site personnel at FU4. Subjects should be instructed to contact the investigator and/or site personnel immediately if the result of the self-pregnancy test is positive. A serum pregnancy test will be performed whenever a urine pregnancy test yields a positive result.

⁶ HBsAg, anti-HBc, and anti-HBs will be assessed at screening in all subjects. For all anti-HBc positive subjects, HBV DNA will also be assessed at screening, and both HBV DNA and HBsAg will be monitored during the trial.

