¹⁴ Subjects in Arm 1 (8-week treatment arm) will proceed to FU4 as TW8 is their EOT visit. Subjects in Arm 2 (12-week treatment arm) will proceed to FU4 as TW12 is their EOT visit.

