7.1.5.4 Drug Administration

Following completion of the Day 1 procedures and confirmation of eligibility, the site pharmacist or study coordinator will contact the IVRS for assignment of the drug regimen to be administered and duration of treatment. Sites should not call IVRS for drug administration until the subject has met all criteria for the study and are ready to receive the first dose of study medication on Day 1.

The first dose of prescribed study medications should be administered at the Day 1 visit.

Subjects who discontinue therapy in the trial prior to the last scheduled treatment visit should have an Early Discontinuation visit and then continue into follow-up visits.

At a minimum, collect the following information when a subject discontinues:

- The reason the subject discontinued
- The date of the last dose of study medications from the trial
- The date of the last assessment and/or contact. A follow-up contact (telephone or visit) will be arranged as appropriate
- (Serious) Adverse events

Final Assessments:

- Every effort should be made to ensure that all procedures and evaluations scheduled for the Early Discontinuation Visit are performed.
- Retrieve all study medications from the subject.

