7.1.5.5 Follow-Up Visits

At the completion of study therapy subjects will return to the study site for follow-up visits at 4, 12, and 24 weeks after the last dose of study drug.

Subjects who discontinue because they have met criteria for virologic failure (Section 4.2.3.1.1.2) while on study therapy should complete an Early Discontinuation Visit as outlined in the Trial Flow Chart (Section 6.0), and return to the study site for follow-up visits at 4, 12, and 24 weeks following confirmation of virologic failure. Subjects who meet the virologic failure criterion for relapse (HCV RNA \geq LLOQ following the end of all study therapy, after becoming undetectable [TND] at the end of treatment) will return to the study site for the remainder of their follow-up visits (e.g., 4, 12, and 24 weeks) as outlined in the Trial Flow Chart (Section 6.0).

Subjects who discontinue for reasons other than virologic failure should complete an Early Discontinuation Visit as outlined in the Trial Flow Chart and return to the study site for follow-up visits at 4, 12, and 24 weeks following the discontinuation of treatment.

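### HBsAg and HBV DNA are not scheduled at the Early Discontinuation visit, so anti-HBc-positive subjects who stop drug between visits and stay in the trial have no scheduled HBV test at stopping (minor; cheap safety improvement)

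*Combined protocol and SAP*

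**What the plan says.** Section 7.1.3.4 has anti-HBc-positive subjects tested for HBV DNA at screening and followed with HBV DNA and HBsAg afterwards: "The results of these assessments will be used to determine HBV reactivation, which will be reported as an Event of Clinical Interest". Section 7.2.3.2 (item 4) defines reactivation and sets a 24-hour reporting duty that runs to 14 days after treatment ends. Section 8.4.1.2 makes the proportion with reactivation an exploratory endpoint.

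The schedule is in the Section 6.0 flow chart. Under "HBV Evaluations", HBsAg and HBV DNA are marked at Visits 1 to 8 (screening, Day 1, TW4, TW8, TW12, FU4, FU12, FU24). Visit 9 (virologic failure confirmation) and Visit 10 (Early DC) are blank. Footnote 6 adds only that, for anti-HBc-positive subjects, "both HBV DNA and HBsAg will be monitored during the trial".

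Completers reach end of treatment at a visit with HBV sampling. For Arm 1, footnote 14 says "Subjects in Arm 1 (8-week treatment arm) will proceed to FU4 as TW8 is their EOT visit"; for Arm 2 the visit is TW12. Early stoppers take another path. Under Section 7.1.5.4, those who discontinue "prior to the last scheduled treatment visit should have an Early Discontinuation visit and then continue into follow-up visits". Under Section 7.1.5.5, those who stop for a reason other than virologic failure "return to the study site for follow-up visits at 4, 12, and 24 weeks following the discontinuation of treatment", and on-treatment virologic failures "return to the study site for follow-up visits at 4, 12, and 24 weeks following confirmation of virologic failure".

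**The concern.** Early DC is in effect the end-of-treatment visit for a subject who stops early. Every other assessment repeated at TW4, TW8 and TW12, apart from dispensing drug, is also marked there: medication review, diary, physical examination, vital signs, birth control, adverse events, coagulation, chemistry and hematology, pregnancy test and HCV RNA. Only the two HBV tests are missing, and the protocol gives no reason.

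What is at stake is patient safety, on a small scale. If reactivation is already present when the subject stops, no scheduled test finds it at stopping or in the following 14 days, which is the period in which the sponsor asks for rapid reporting. In a completer the end-of-treatment sample would find it.

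**Working it through.** **1. Are the blanks real?** The chemistry and hematology row carries ten marks, one per visit. The HBsAg and HBV DNA rows carry eight, ending at FU24. The two unscheduled visits are therefore blank.

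**2. Does other text supply the test?** No.
- Footnote 6 and Section 7.1.3.4 speak of monitoring in general terms, and Table 12 refers only to certain later visits.
- Section 7.1.5.4 asks for what is scheduled at Early DC, and HBV tests are not.
- Section 7.1.4.1 requires final-visit activities from a subject who leaves the trial. FU24 includes HBV tests, so that subject is covered. One who stops drug but stays in follow-up is not.

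**3. Time to the next scheduled test after a non-virologic stop.** FU4 has a window of -1 to +2 weeks: 28 - 7 = 21 days to 28 + 14 = 42 days after stopping. Both exceed 14 days.

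**4. Interval between consecutive HBV samples, stop between TW4 and TW8.** Days are counted from first dose, and Early DC is assumed to fall on the day of stopping. TW4 is day 28 (window -7 to +7 days, earliest day 21). TW8 is day 56 (window -7 to +14 days, days 49 to 70).

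| Case | As planned | With an Early DC sample |
|---|---|---|
| Nominal, stop on day 29 to 55 | FU4 on day 57 to 83; 57 - 28 = 29 to 83 - 28 = 55 days | at most max(55 - 28, 28) = 28 days |
| Windows, stop by day 48 (TW8 window not yet open) | FU4 by 48 + 42 = day 90; 90 - 21 = 69 days | max(48 - 21, 42) = 42 days |
| Windows, TW8 still pending, stop on day 69 | FU4 by 69 + 42 = day 111; 111 - 21 = 90 days | max(69 - 21, 42) = 48 days |

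The last row is in practice an Arm 2 case, because the Arm 1 course is 8 x 7 = 56 days unless dosing was interrupted.

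**5. Comparators already in the plan.**
- Completer, end-of-treatment sample to FU4: 28 days nominal. With TW8 taken on day 49 and FU4 at 56 + 42 = day 98, it is 98 - 49 = 49 days.
- FU4 to FU12: 8 x 7 = 56 days nominal; with windows (84 + 14) - (28 - 7) = 77 days.
- FU12 to FU24: 12 x 7 = 84 days nominal; with windows (168 + 14) - (84 - 14) = 112 days.

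**6. How many subjects?** In Table 3, among subjects given 12 weeks of EBR+GZR without ribavirin, discontinuations due to an adverse event were 0/56 (treatment-naïve) and 1/9 (treatment-experienced). That is 1/65 = 1.5%, Clopper-Pearson 95% CI 0.04% to 8.3%. The table lists only stops that ended in non-SVR. The documents give no anti-HBc prevalence, so 10-30% is assumed.
- At 1/65: 120 x 1/65 x 0.10 = 0.18 to 120 x 1/65 x 0.30 = 0.55 subjects.
- At assumed early-stop rates of 1-5%: 120 x 0.01 x 0.10 = 0.12 to 120 x 0.05 x 0.30 = 1.8 subjects.

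These counts include stops that fall on a scheduled visit, so the group with the gap is smaller.

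**The case against.** The strongest reply is that no study result changes. SVR12 does not depend on HBV tests. The Section 8.4.1.2 proportion has no date limit, so a reactivation first seen at FU4 still counts. The nominal interval of 29 to 55 days is shorter than the off-drug spacing the plan accepts. With windows, 69 days is below both the 77 and the 112 days of planned follow-up, and about 90 is below the 112. All of this stands, and it keeps the point minor. It does not address the difference at stopping itself, where completers are sampled and these subjects are not.

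The second reply is that safeguards exist, and several do narrow the gap.
- An enzyme rise found at TW4, TW8 or TW12 comes with a same-visit HBV sample, and Section 5.8.1 asks for its confirmation within one week.
- ALT and AST are measured at Early DC. The note in Section 7.2.3.2 says that enzyme thresholds may call for a search for the cause, under site guidance that is not in the documents. Section 7.1.5.6 requires weekly returns when laboratory criteria are met at the last dosing visit.
- Sections 4.2.3.2 and 7.1 allow unscheduled testing.

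None of these guarantees an HBV test at stopping.

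On-treatment virologic failure is a milder form of the same gap. It is detected on HCV RNA drawn at visits that also have HBV sampling. Rebound, for example, is a rise "from nadir while on treatment and confirmed from a separate blood draw within 2 weeks", and FU4 is then timed from confirmation. From the visit sample to FU4 is up to 14 + 28 = 42 days nominal.

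A reader might infer that the plan contradicts itself, or that every early stopper goes untested. The documents support neither. Table 12 promises only certain visits. Subjects who leave the trial, or who stop at a scheduled visit, have an HBV sample provided for.

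**Conclusion.** The gap holds as a minor schedule omission. An anti-HBc-positive subject who stops drug between scheduled visits and stays in the trial has no scheduled HBV test at stopping. After a non-virologic stop, none falls inside the 14-day reporting period either. The blank cells and the 21-to-42-day delay are certain from the text. The interval sizes rest on Early DC falling on the day of stopping and, for the extremes, on full use of the visit windows. The count, under about 1 of 120 subjects at the 1/65 rate, rests on the assumed prevalence and on one observed stop.

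Two further inferences would go too far. A reader might infer that reactivations in early stoppers are lost to the analysis, but the exploratory proportion still counts them at FU4 or later. A reader might also infer that an Early DC sample closes the reporting limit. It helps only where reactivation is already present at stopping. One that begins later and is first seen at FU4 falls outside the 14 days for completers as well, which is a separate matter.

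**What to change.** In the Section 6.0 flow chart, mark HBsAg and HBV DNA at Visit 10 for anti-HBc-positive subjects, under the existing footnote 6. No change to the reactivation definition or the endpoint is needed, because neither Section 7.2.3.2 nor Section 8.4.1.2 restricts reactivation to particular visits. The cost is two marks, about 10 mL of blood per subject (the per-visit HBV volume in Section 12.5) and two assays already in use, in a few subjects at a visit where blood is drawn anyway.

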7.1.3.5 Planned Genetic Analysis Sample Collection

Sample collection, storage and shipment instructions for Planned Genetic Analysis samples will be provided in the operations/laboratory manual.

7.1.3.6 Future Biomedical Research Sample Collection

The following specimens are to be obtained as part of Future Biomedical Research:

Leftover DNA for future research; leftover plasma from HCV RNA for future research; and leftover plasma from viral resistance and biomarkers for future research.

7.1.4 Other Procedures

7.1.4.1 Withdrawal/Discontinuation

Subjects who discontinue/withdraw from treatment prior to completion of the treatment regimen should be encouraged to continue to be followed for all remaining study visits.

When a subject discontinues/withdraws from participation in the trial, all applicable activities scheduled for the final trial visit should be performed at the time of discontinuation. Any adverse events which are present at the time of discontinuation/withdrawal should be followed in accordance with the safety requirements outlined in Section 7.2 - Assessing and Recording Adverse Events.

7.1.4.1.1 Withdrawal From Future Biomedical Research

Subjects may withdraw their consent for Future Biomedical Research and have their specimens and all derivatives destroyed. Subjects may withdraw consent at any time by contacting the principal investigator for the main trial. If medical records for the main trial are still available, the investigator will contact the Sponsor using the designated mailbox ([contact]), and a form will be provided by the Sponsor to obtain appropriate information to complete specimen withdrawal. Subsequently, the subject's specimens will be removed from the biorepository and be destroyed. A letter will be sent from the Sponsor to the investigator confirming the destruction. It is the responsibility of the investigator to inform the subject of completion of destruction. Any analyses in progress at the time of request for destruction or already performed prior to the request being received by the Sponsor will continue to be used as part of the overall research trial data and results. No new analyses would be generated after the request is received.

In the event that the medical records for the main trial are no longer available (e.g., if the investigator is no longer required by regulatory authorities to retain the main trial records) or the specimens have been completely anonymized, there will no longer be a link between the subject's personal information and their specimens. In this situation, the request for specimen destruction cannot be processed.

7.1.4.2 Blinding/Unblinding

This is an open label trial; there is no blinding for this trial.

7.1.4.3 Calibration of Equipment

The investigator or qualified designee has the responsibility to ensure that any device or instrument used for a clinical evaluation/test during a clinical study that provides information about inclusion/exclusion criteria and/or safety or efficacy parameters shall be suitably calibrated and/or maintained to ensure that the data obtained is reliable and/or reproducible. Documentation of equipment calibration must be retained as source documentation at the study site.

7.1.5 Visit Requirements

Visit requirements are outlined in Section 6.0 - Trial Flow Chart. Specific procedure-related details are provided above in Section 7.1 - Trial Procedures.

7.1.5.1 Screening

Up to 45 days prior to randomization/treatment allocation, potential subjects will be evaluated to determine that they fulfill the entry requirements as set forth in Section 5.1. Verification should be obtained to confirm the subject's cirrhosis status and the subject's fibrosis score must be captured to support secondary data analysis.

Documentation of prior IFN +/- RBV +/- SOF treatment history must include clinic notes or referral letter documenting regimen administered, approximate dates of treatment, approximate date of virologic failure, and a history of laboratory confirmed prior virologic

failure or documented intolerance to allow for one of the following categorizations (if the subject was treated with a PR regimen more than once, the categorization must be based on the most recent round of treatment):

1. HCV Treatment-Naïve: defined as no prior exposure to any interferon, ribavirin, or other approved or experimental HCV-specific direct-acting antiviral agent.
2. HCV Treatment-experienced: defined as any prior treatment with an IFN regimen (IFN or peg-IFN +/- RBV) or sofosbuvir (SOF) + RBV or SOF + peg-IFN + RBV that did not result in a sustained virologic response (SVR)

All TE patients will be classified into one of the following categories:

- I. Prior On-Treatment Failures (may be one or more of the following):
 - i. Non-Responder: Subject has HCV RNA detected at end of prior treatment without HCV RNA <LLOQ on treatment.
 - ii. Null Responder: <2 log₁₀ IU/mL reduction in HCV RNA after at least 12 weeks of a IFN regimen OR <1 log₁₀ IU/mL reduction in HCV RNA after 4 weeks and discontinued therapy prior to treatment-week 12.
 - iii. Breakthrough: Subject has a confirmed HCV RNA \geq LLOQ [TD(q)] while on prior treatment after being <LLOQ previously.
 - iv. Partial Responder: \geq 2 log₁₀ IU/mL reduction in HCV RNA after at least 12 weeks of treatment, but not achieving HCV RNA target not detected at end-of-treatment, with prior regimen.
- II. Relapser: HCV RNA target not detected at end-of-treatment after prior regimen, but HCV RNA quantifiable (\geq LLOQ) during follow-up.
- III. Intolerant to Prior Regimen: \geq 4 weeks of prior regimen and no more than 80% of treatment duration:
 1. \leq 20 weeks for a 24 week treatment regimen
 2. \leq 40 weeks for a 48 week treatment duration
- IV. Otherwise not Classified/Unknown response to Prior Regimen: Subject received at least one dose of prior regimen and stopped for any other reason not listed above

The investigator will discuss with each potential subject the nature of the study, its requirements, and its restrictions. Screening procedures may be repeated after consultation with the Sponsor.

Subjects will be instructed that they are required to use an acceptable method of birth control (see Subject Inclusion Criteria Section 5.1.2) from at least 2 weeks prior to Day 1, throughout treatment, and 14 days after the last dose of study medication, or longer if dictated by local regulations, for women and men, respectively.

Subjects will be instructed about the restrictions for concomitant medications, as noted in Section 5.5.

All screening procedures listed for Visit 1 in the Trial Flow Chart must be completed and subject eligibility confirmed by the investigator prior to the subject's randomization/allocation and drug administration.

All subjects will be given a Subject Identification Card (Section 7.1.1.3), at the time of screening, identifying them as participants in a research study. The Subject Identification Card will contain contact information (including direct telephone numbers) to be utilized in the event of an emergency.

